10.2.1. Adverse Events of Special Interest

TEAEs of special interest will be summarized and may include the terms or categories noted below. The list of PTs of special interest will be reviewed and finalized prior to each database extraction for analyses specified in section 5.6.

- Anxiety
- Confusion
- Convulsions
- Depressed consciousness
- Depression and suicidality
- Psychotic and dissociative disorders
- Impaired attention or cognitions
- Parasomnias
- Respiratory failure and respiratory depression
- Drug Abuse
- Accidents and Injuries

10.2.2. Additional Adverse Event Analyses

The subject incidence of TEAEs up to 30 days after last dose (excluding AEs during the DBRW for those randomized to Placebo as well as AEs up to 30 days after last dose of Placebo for those not entering OLE) by 4 week intervals across the study will be summarized by Baseline Medication Group and overall using the SAF. Additionally, results will be presented for week 1, week 2, week 3, and week 4 during the OTTP. These analyses will be summarized by SOC and PT. A subject will be counted in each interval (once per onset) that a TEAE occurred within the interval and the denominator for the interval is based on the number of subjects who were exposed to study drug at the start of the interval. Ongoing TEAEs will only be counted once in the interval of onset.

The subject incidence of TEAEs by SOC and PT during the 30 day period after the last dose of JZP-258 will be summarized by Baseline Medication Group and overall using the SAF. This summary will exclude adverse events during the 30 day period after the last dose of Placebo for those randomized to Placebo who did not receive study drug during the OLE.

Additional adverse event summaries for those subjects exposed to a single dose of JZP-258 of > 4.5g at any time during the study will be provided and compared against the full SAF analysis set. The group of subjects' exposure to a single dose of JZP258 of > 4.5g can include receiving any dose regimen, as long as one of the doses was > 4.5g.

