5. STUDY TREATMENT(S)

5.1. Description of Study Drug

Study Drug: JZP-258 mixed oxybate salts oral solution, 0.5 g/mL

Placebo (for Double-blind Randomized Withdrawal Period only): A matching oral solution to JZP-258 will be provided. The placebo formulation is an aqueous solution consisting of sodium citrate, malic acid, and sucralose. All ingredients are compendial (USP/NF).

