All subjects will undergo at minimum a 10-week OTTP even if the optimized dose and regimen is achieved earlier. Every effort should be made to titrate to an optimally effective and tolerable dose and regimen within the first 8 weeks, and maintain an unchanged dose of JZP-258 for at least 2 weeks prior to entering the SDP. Any subject for whom an efficacious and tolerable dose and regimen is not established within the first 10 weeks may undergo up to an additional 4-weeks of titration/adjustment with approval from the Medical Monitor. Subjects who are unable to attain an efficacious and tolerable dose and regimen after 14 weeks will be withdrawn from the study.

Subjects who have reached an optimized dose and regimen, and who have completed the OTTP, will then enter the 2-week SDP.

Stable Dose Period (2 weeks)

Subjects will remain on the stable JZP-258 dose, unchanged, during this 2-week period. Upon completion of the SDP, subjects will be assessed for randomization eligibility.

Double-blind Randomized Withdrawal Period (2 weeks)

Subjects who meet the randomization eligibility criteria at the end of the SDP will be randomized if the following conditions are met at the End of Stable Dose Visit:

- The dose and regimen of JZP-258 remains unchanged during the SDP, and subjects demonstrate adequate compliance with dosing.
- No ongoing adverse events (AEs) occur due to JZP-258 treatment that would require dose adjustment or treatment discontinuation during the DBRW.
- Subjects who are on Xyrem at study entry must have PGIc scale ratings at the end of the SDP of no change, minimal, much, or very much improved compared with the Baseline Visit.
- Subjects who are not on Xyrem at study entry must have PGIc scale ratings of minimal, much, or very much improved compared with the Baseline Visit and a lower ESS score at the end of the SDP compared with the Baseline Visit.

Eligible subjects are randomized 1:1 to receive 1 of the following 2 treatments during the 2-week DBRW.

- JZP-258: Active JZP-258 will be continued as a double-blind (DB) treatment at the stable dose and regimen for 2 weeks.
- Placebo: Placebo will be initiated as a DB treatment at a volume and regimen equivalent to the JZP-258 dose and regimen for 2 weeks.

Open-label Safety Extension Period (24 weeks)

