5.3. Study Treatment

During the OTTP, all subjects will receive open-label JZP-258 and are titrated to a tolerable and efficacious dose based on the recommendations summarized in Table 1.

Table 1: JZP-258 Dosing Recommendations

Dosing Regimen	Starting Nightly Dose	Titration Increments	Maximum Nightly Dose ^b
Once Nightly	≤3 g	≤1.5 g/night per week	6g
Twice Nightly	≤4.5 g (divided)	≤1.5 g/night per week	9g
Thrice Nightly (titration only, not a starting dose)	Not applicable	≤1.5 g/night per week	9g

Note: the aim of JZP-258 dose titration and optimization is to maximize efficacy (reduced IH symptoms, e.g. EDS, sleep inertia, and sleep duration) while ensuring adequate nocturnal sleep and minimizing risks associated with safety and tolerability

^aThe weekly increase in dose of ≤1.5 g/night may be made incrementally every few days as tolerated

^bThe maximum single dose should not exceed 6 g and the maximum nightly dose should not exceed 9 g at twice or thrice nightly dosing

EDS=excessive daytime sleepiness; IH=idiopathic hypersomnia

During the SDP, all subjects will receive open-label JZP-258 at the same unchanged dose that they received at the end of the OTTP.

During the DBRW, all subjects will receive blinded study drug. At the end of the SDP, subjects will enter the DBRW and will be randomized 1:1 to receive either JZP-258 (at the dose taken at the end of the SDP) or Placebo (at a volume and regimen equivalent to the JZP-258 dose taken at the end of the SDP).

During the OLE all subjects will receive open-label JZP-258. During the PK study, all enrolled subjects will receive open-label JZP-258 with no change in dose required.

Study drug will be dispensed at clinic visits and, if applicable, at intervals specified by state or local regulations or to resolve logistical issues.

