10.1. Exposure

10.1.1. Extent of Exposure

The below exposure information will be summarized based on the SAF using descriptive statistics as well as counts and percentages, as appropriate, depending on the study period. Exposure summaries are based on data collected by the study drug administration eCRF.

- **Across all periods overall and by Baseline Medication Group:** average of total nightly dose of JZP-258 (in g/night), duration of exposure to single doses of JZP-258 > 4.5g, duration of study drug exposure in days, and duration of exposure to JZP-258 in days (excludes time subjects received Placebo in DBRW);
- **Across all periods by Stable Dose Regimen (once nightly vs twice nightly):** starting dose regimen of JZP-258 in OTTP (once, twice, or thrice nightly), time to get to total nightly stable dose (in days), average of total nightly dose of JZP-258 (in g/night), and duration of exposure to JZP-258 (in days);
- **OTTP overall and by Baseline Medication Group:** total nightly starting dose of JZP-258 (in g/night), average of total nightly dose of JZP-258 (in g/night), starting dose regimen of JZP-258 (once, twice, or thrice nightly), number of dose adjustments, time to get to total nightly stable dose (in days), and duration of exposure (in days) regardless of the JZP-258 total nightly received dose;
- **SDP overall and by Baseline Medication Group:** average of total nightly dose of JZP-258 (in g/night) and duration of exposure (in days) regardless of the JZP-258 total nightly received dose;
- **DBRW overall and by Baseline Medication Group:** JZP-258 total nightly received dose (in g/night), and duration of study drug exposure (in days) regardless of the study drug total nightly received dose;
- **SDP and DBRW by Randomized Treatment group:** JZP-258 total nightly received dose (in g/night), duration of exposure (in days) regardless of the JZP-258 total nightly received dose in SDP, and duration of study drug exposure (in days) regardless of the study drug total nightly received dose in DBRW;
- **OLE overall and by Baseline Medication Group:** average of total nightly dose of JZP-258 (in g/night) and duration of exposure (in days) regardless of the JZP-258 total nightly received dose

Exposure summaries reflect all dose changes entered on the study drug administration eCRF. Data from the dosing diary and compliance are not considered for duration of exposure.

Listings of study drug exposure and of the dosing diary will be presented.

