Only TEAEs are included in summary tables unless otherwise specified. If a subject has multiple episodes of events coded to the same SOC or PT, then the subject will be counted just once in the summaries for that term. Subject incidence of TEAEs by SOC and PT tables are sorted by SOCs (alphabetical order) and then by PTs (descending order) within each SOC for the overall frequency. For summaries by PT only, PTs will be sorted in descending order of overall frequency.

Each TEAE summary will have two sets of outputs:

- TEAEs by baseline medication group across the entire study (excluding adverse events during the DBRW for those randomized to Placebo) up to 30 days after last dose using the SAF

- TEAEs during the DBRW by randomized treatment group using the DBRW SAF. Adverse events are included as TEAEs up to 30 days after the last dose date or the first dose date in the OLE period, whichever is earlier.

A general overall summary of TEAEs with the number and percent of subjects who experienced the following types of events will be provided:

- Subjects with any TEAE
 - Subjects with any related TEAE
- Subjects with any serious TEAE
- Subjects with TEAE by severity
- Subjects with an AE outcome as death
- Subjects with any TEAE leading to study drug discontinuation
- Any TEAE leading to study drug dose reduction
- Any TEAE leading to study drug dose increase
- Any TEAE leading to study drug dose interruption
- Any TEAE not recovered

Subject incidence of TEAEs tables will be summarized by the following:

- SOC and PT
 - TEAE reported $\geq 2\%$ of by SOC and PT
- PT only
- Maximum severity by SOC and PT
- Treatment-related by SOC and PT
- TEAEs of special interest by category (defined in section 10.2.1) and PT
- TEAEs leading to permanent withdrawal of study drug by SOC and PT

Separate adverse event listings will be provided including the following:

- All adverse events
- Adverse events with an outcome of death
- Adverse events leading to permanent withdrawal of study drug
- Serious adverse events
- Adverse events of special interest, defined in section 10.2.1

Non-TEAEs will be flagged in the listings.

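### The 4-week TEAE table in SAP 10.2.2 drops placebo-arm DBRW events from the numerator but keeps those subjects in the denominator, so it understates JZP-258 incidence in the intervals that overlap the DBRW

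*SAP*

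**What the plan says.** SAP 10.2.2 presents subject incidence of TEAEs "by 4 week intervals across the study will be summarized by Baseline Medication Group and overall using the SAF". The randomized arms are therefore pooled within each column.

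- **Numerator.** The count is made "excluding AEs during the DBRW for those randomized to Placebo as well as AEs up to 30 days after last dose of Placebo", the last part applying to subjects who do not enter the open-label extension (OLE).
- **Denominator.** The rule is that "the denominator for the interval is based on the number of subjects who were exposed to study drug at the start of the interval". Nothing takes placebo subjects or placebo time out of it.
- **Meaning of *study drug*.** SAP 5.3 states: "During the DBRW, all subjects will receive blinded study drug". SAP 10.1.1 lists two separate exposure measures, "duration of study drug exposure in days, and duration of exposure to JZP-258 in days (excludes time subjects received Placebo in DBRW". Only the second removes placebo time, so the first must include it.

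SAP 10.2 also plans a whole-study TEAE summary on the safety set, "excluding adverse events during the DBRW for those randomized to Placebo", and a separate DBRW summary by randomized arm.

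**The concern.** The interval table exists to show whether adverse events on JZP-258 fade, persist or recur. Its numerator covers JZP-258 time only, while its denominator counts people who spent part of the interval on placebo. The two do not describe the same exposure.

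The mismatch falls where about half of the randomized subjects stop the drug. A fall in reported incidence at that point could be read as events fading when part of it comes from the counting rule. Because the arms are pooled in the table, a reader cannot separate the two.

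**Working it through.** **Inputs.**
- Allocation: "Eligible subjects are randomized 1:1 to receive 1 of the following 2 treatments during the 2-week DBRW" (SAP 5.1).
- 56 subjects per arm, 112 in total (SAP 5.4).
- Titration 10 to 14 weeks, Stable Dose Period 2 weeks, DBRW 2 weeks (SAP 5.1). The end-of-DBRW visit window is 14 to 17 days (Protocol Appendix 1.1).
- True 4-week TEAE incidence on JZP-258, *p*: not in the documents. I assume a range of 5% to 50% and a constant hazard.

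**The plan's own figures.** The documents give no interval incidence to reproduce. The arm sizes used here are the planned ones. With a difference of 3.5, an SD of 5.5, two-sided 0.05 and one O'Brien-Fleming-type look at 60% information, 56 per arm gives 91.84% power (stated: 91.8%). 112/(1 - 0.20) = 140, as stated.

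**Where the DBRW falls.** It starts after titration plus 2 weeks, that is, after 12 to 16 weeks. Counting 4-week intervals from first dose:

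| Titration (weeks) | DBRW weeks | Interval(s) | On what at interval start |
|---|---|---|---|
| 10 | 13-14 | 13-16 | starting blinded treatment |
| 11 | 14-15 | 13-16 | JZP-258 |
| 12 | 15-16 | 13-16 | JZP-258 |
| 13 | 16-17 | 13-16 and 17-20 | JZP-258, then blinded treatment |
| 14 | 17-18 | 17-20 | starting blinded treatment |

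In every row the placebo-arm subject is in the denominator, and about 14 days of events are removed from one interval or split over two.

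**Time at risk, if every DBRW falls wholly in one interval.** JZP-258 subject-weeks are 56×4 + 56×2 = 336. The denominator implies 112×4 = 448. 336/448 = 75%.

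**Displayed incidence.** A placebo-arm subject has 14 of 28 days in which an event can count, so q = 1 - (1 - p)^(14/28). The table shows (56p + 56q)/112.

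| Assumed p | q | Shown | Relative shortfall |
|---|---|---|---|
| 5% | 2.5% | 3.8% | 24.7% |
| 10% | 5.1% | 7.6% | 24.3% |
| 20% | 10.6% | 15.3% | 23.6% |
| 30% | 16.3% | 23.2% | 22.8% |
| 50% | 29.3% | 39.6% | 20.7% |

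**Sensitivity.** With a 17-day DBRW the exponent is 11/28 and the shortfall is 26% to 30%. With the DBRW split evenly over two intervals, 21 of 28 days remain in each. At p = 20%, q = 1 - 0.8^0.75 = 15.4% and the table shows (20% + 15.4%)/2 = 17.7%, a shortfall of about 11% in each interval.

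**The other reading of *study drug*.** Suppose it meant JZP-258 only and the interval opened with the DBRW. The 56 placebo subjects would leave the denominator, while their events after restarting JZP-258 in the OLE would still count. At p = 20% the numerator is 56×0.20 + 56×0.1056 = 17.1, and 17.1/56 = 30.6%. That overstates the risk.

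**The case against.** **The term is not settled.** Protocol 5.1 has the entry "Study Drug: JZP-258 mixed oxybate salts oral solution, 0.5 g/mL" and lists placebo separately, so the denominator might mean JZP-258 only. SAP 5.3 and 10.1.1 make this the weaker reading for an SAP table. It would not rescue the table either, because the error then runs the other way. What stands is that the term needs defining.

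**The size is illustrative.** This stands. The event rate and constant hazard are assumptions, and so is placing every DBRW in one interval. Visit windows in Protocol Appendix 1.1 allow the DBRW to start from about day 77 (63 + 14) to day 115 (98 + 17), so a few subjects could also touch weeks 9-12. Protocol 7.2 expects most titrations to end at Week 10, which makes concentration in weeks 13-16 plausible but not complete. More events on restarting JZP-258 would offset part of the dip.

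**Other outputs cover the gap.** This largely stands. The by-arm DBRW summary in SAP 10.2 has a matched denominator. A reader might infer that the whole-study summary shares the denominator fault. It does not, because every subject in the safety set received JZP-258 during titration.

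**The whole-study table and events after placebo.** A reader might also infer that this table wrongly assigns to JZP-258 the events after the last placebo dose in subjects who skip the OLE, since it excludes placebo-arm events only within the DBRW. The documents do not establish that. The next item in SAP 10.2 carries DBRW events up to 30 days after the last dose or to the first OLE dose, whichever is earlier, so the exclusion may already cover that tail. Two things point the other way: SAP 10.2 has a separate safety follow-up class, and 10.2.2 names the tail as an addition. The wording is ambiguous, and misattribution is not shown.

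**Conclusion.** The mismatch and its direction follow from the SAP's own text: on its use of *study drug*, the interval table understates JZP-258 incidence wherever an interval overlaps the DBRW. The shortfall of about a fifth to a quarter applies only to the illustrated case (14-day DBRW wholly inside one interval for all 112 subjects, constant hazard). It should not be read as a forecast of the dip in weeks 13-16.

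The consequence is limited to how one supplementary safety table is read. SAP 7.4 and 10 plan no inference on safety data, and efficacy, type I error and power are untouched. The point about SAP 10.2 is a clarification affecting few subjects, since those who complete the DBRW go on to the OLE.

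**What to change.** 1. In SAP 10.2.2, for intervals that overlap the DBRW, report TEAEs per JZP-258 person-time, excluding placebo time as SAP 10.1.1 already does for exposure. Alternatively, leave placebo-arm subjects out of both numerator and denominator in those intervals. Person-time keeps more data, because it retains placebo-arm subjects' JZP-258 time before and after the DBRW.
2. Do not restrict the denominator alone. Events in placebo-arm subjects after OLE restart would stay in the numerator and could push the figure too high, as in the 30.6% example. Where the subject is still on JZP-258 when the interval opens, a restriction applied at interval start would change nothing.
3. Replace *study drug* in the denominator rule with JZP-258.
4. In SAP 10.2, state explicitly that events up to 30 days after the last placebo dose in subjects not entering the OLE are excluded from the whole-study JZP-258 summary, to match 10.2.2.

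The cost is SAP wording and minor programming. The JZP-258 exposure derivation is already planned, and no new data are needed.

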3.4. Study Duration

The maximum treatment duration of study for each subject will be approximately 38 to 42 weeks. The estimated duration of the study for each subject is approximately 44 to 46 weeks. It is anticipated that enrollment will be completed within approximately 24 months.

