5. STUDY DESIGN

5.1. Summary of Study Design

This is a double-blind, placebo-controlled, randomized withdrawal, multicenter study of the efficacy and safety of JZP-258 oral solution with an open-label safety extension period. JZP-258

drug product is a mixed oxybate salts oral solution being developed as a low sodium alternative product for Xyrem®.

The study consists of the following periods, which are further described below:

- Screening Period for 14 to 30 days, with the option to rescreen once
- Open-label Treatment Titration and Optimization Period (OTTP) for 10 to 14 weeks
- Stable Dose Period for 2 weeks
- Double-blind Randomized Withdrawal Period for 2 weeks
- Open-label Safety Extension Period (OLE) for 24 weeks
- Safety Follow-up Period for 2 weeks

Furthermore, a single overnight PK evaluation will be performed in up to 30 subjects during either the OTTP or the OLE.

Screening Period (14 to 30 days)

All subjects will be evaluated for eligibility during the Screening Period, which will occur over a period of 14 to 30 days.

(Note: Subjects may be allowed to rescreen [once] if they previously did not meet all eligibility requirements.)

Open-label Treatment Titration and Optimization Period (10 to 14 weeks)

The Baseline Visit (Day 1) occurs at the time of initial study drug dispensation. During the OTTP subjects will either transition from Xyrem to JZP-258, or initiate treatment with JZP-258, based on treatment status at study entry:

1. Subjects who are on a stable dose of Xyrem at study entry will switch from Xyrem to the same dosing regimen of JZP-258. The dosing regimen of JZP-258 then may be adjusted until an optimally effective and tolerable dose regimen is established.
2. Subjects who are not on Xyrem at study entry will initiate JZP-258 as either a once or twice nightly dosing regimen at the discretion of the Investigator. The dosing regimen may then be adjusted until an optimally effective and tolerable dosing regimen is established. (Refer to Protocol Section 5.3 for details on dosing and dosing frequency.)

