10.2. Adverse Events

Adverse events (AEs) occurring from the initial subject ICF signature date until the final study visit will be reported. If the Investigator becomes aware of a serious adverse event (SAE) within 30 days after the last dose of study drug, the event must also be reported. In addition, any SAE assessed as related to study drug or procedure by the Investigator must be reported regardless of time after study termination.

AEs will be coded to system organ class (SOC) and preferred term using the Medical Dictionary for Regulatory Activities (MedDRA), Version 19.1. The investigator will assess the relationship of each AE to study drug. AE with a missing relationship to study drug will be reported as related in the summaries. Severity, as determined by the Investigator, will be classed as mild, moderate, severe, life-threatening or fatal. AE with missing severity will be reported as missing in the summaries.

Note that subjects who acquire COVID-19 or report AEs due to the COVID-19 public health emergency (e.g. anxiety) while on study will be coded accordingly and included in the adverse event summaries.

All AEs will be classified according to the period onset as defined by the following:

- Screening AEs are defined as AEs that started on or after the signature of the initial subject ICF but prior to or on the first dose of OTTP study drug
- Treatment period AEs will be defined as occurring in treatment periods (OTTP, SDP, DBRW, and OLE) based on the onset date and the date of first dosing in each of the treatment periods. AEs that occur on the start of the SDP and DBRW are attributed to the previous period.
- Safety follow-up AEs are defined as occurring after the last dose date until 30 days after the last dose date

A treatment-emergent adverse event (TEAE) is defined as any event with onset date on or after the first dose of study drug, including adverse events that occur until 30 days after the last dose date. For the purpose of calculating treatment emergence, incomplete onset dates will be imputed as detailed in Appendix 2.

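### The 4-week-interval TEAE table can count subjects who are off drug in its numerator while leaving them out of its denominator; the effect is minor and falls mainly on weeks 41 to 48

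*SAP*

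**What the plan says.** SAP 10.2.2 (Additional Adverse Event Analyses) defines the table. The numerator is "The subject incidence of TEAEs up to 30 days after last dose", leaving out placebo-related events, and it is presented "by 4 week intervals across the study will be summarized by Baseline Medication Group and overall using the SAF", with the first four OTTP weeks also shown singly. For each interval, "the denominator for the interval is based on the number of subjects who were exposed to study drug at the start of the interval".

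The 30-day tail agrees with SAP 10.2, which defines a TEAE as an event on or after first dose, "including adverse events that occur until 30 days after the last dose date". The next paragraph of 10.2.2 plans a separate table for the 30 days after the last JZP-258 dose.

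Neither section says how a subject who is off drug but inside the 30-day window is counted in an interval, or where the series of intervals ends.

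**The concern.** The numerator and denominator describe different groups of subjects. In the other TEAE tables the denominator is a fixed safety set (the SAF or the DBRW SAF), so a 30-day tail does no harm. Here the denominator shrinks as subjects finish, while the tail still adds events.

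Completers finish at roughly the same time, so the mismatch gathers in the last intervals. The table is also split by baseline medication group, SOC and PT, which divides a small late denominator further. A higher late percentage made up partly of off-drug events could be misread as an effect of longer treatment.

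**Working it through.** **Treatment duration.** SAP 5.1 gives "Open-label Treatment Titration and Optimization Period (OTTP) for 10 to 14 weeks", "Stable Dose Period for 2 weeks", "Double-blind Randomized Withdrawal Period for 2 weeks" and a 24-week extension. So 10+2+2+24 = 38 weeks and 14+2+2+24 = 42 weeks. This reproduces Protocol 3.4: "The maximum treatment duration of study for each subject will be approximately 38 to 42 weeks". Nominal last-dose days are 266, 280 and 294 for titration of 10, 12 and 14 weeks. Protocol 7.2 expects titration to end at Week 10 for most subjects, so most completers stop near day 266.

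**Intervals.** Interval 10 is days 253-280, interval 11 (weeks 41-44) is days 281-308, and interval 12 (weeks 45-48) is days 309-336.

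**AE capture.** Under Protocol 6.15.6 and SAP 10.2, all AEs are recorded to the final study visit, which is 2 weeks after the extension. After that only SAEs must be reported: those the investigator learns of within 30 days of last dose, and related SAEs at any time. Both a 14-day and a 30-day tail are therefore examined.

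**Method.** At a constant event rate, inflation = (all person-days that can supply an event) / (person-days of subjects in the SAP denominator). Let s10, s12 and s14 be the shares with 10-, 12- and 14-week titration. The documents do not give these shares, so they are assumptions.

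**Interval 11, nominal schedule.** Only 14-week subjects are on drug at day 281.

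- 14-day tail: windows end on days 280, 294 and 308, so the days falling in interval 11 are 0, 14 and 28. Inflation = (14·s12 + 28·s14)/(28·s14) = 1 + 0.5·(s12/s14). That is 1.0 if nobody ends at 12 weeks and 1.5 if the two extended shares are equal.
- 30-day tail: windows end on days 296, 310 and 324, so the days are 16, 28 and 28. Inflation = (16·s10 + 28·s12 + 28·s14)/(28·s14).

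| s10/s12/s14 (%) | 14-day tail | 30-day tail |
|---|---|---|
| 90/5/5 | 1.5 | (14.4+1.4+1.4)/1.4 = 12.3 |
| 80/10/10 | 1.5 | (12.8+2.8+2.8)/2.8 = 6.6 |
| 60/20/20 | 1.5 | (9.6+5.6+5.6)/5.6 = 3.7 |
| 40/30/30 | 1.5 | (6.4+8.4+8.4)/8.4 = 2.8 |
| 50/0/50 | 1.0 | (8+14)/14 = 1.6 |

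If nobody is extended, the denominator is zero. If all have 14 weeks, inflation is 1.0.

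**Interval 11 with visit windows.** Visit days were simulated within the ranges in Protocol Appendix 1.1 and 1.2. For 5, 10, 20, 40 and 60% extended, inflation is about 3.9, 2.7, 1.9, 1.4 and 1.3 with the 14-day tail. With the 30-day tail it is about 9.1, 6.2, 3.9, 2.3 and 1.7. These values depend on how visits are assumed to spread within the windows.

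**Interval 12.** The latest nominal last dose is day 294. At the window limits it is 98+17+17+175 = day 307. Nobody is on drug at day 309, so the denominator is zero in every scenario. With the 30-day tail, 12- and 14-week subjects can still contribute events to days 310 and 324. With the 14-day tail and nominal timing the interval is empty.

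**Earlier intervals.** In interval 10, completers are in both numerator and denominator (ratio 1.0). For early stoppers, take the plan's 20% loss before randomization (140 − 112 = 28) and assume it is even over 12 weeks, or about 9.3 per interval. A stopper carries on average 3.5 days (14-day tail) or about 15.9 days (30-day tail) into the next interval. That adds 9.3×3.5 ≈ 33 or 9.3×15.9 ≈ 148 person-days to between 112×28 = 3,136 and 131×28 = 3,668. The increase is about 1% or 4 to 5%.

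**The case against.** The strongest reply concerns size. Thirty days is an outer limit for calling an event treatment-emergent, not a collection period for all AEs. Ordinary AEs stop at the 2-week final visit. A 10-week-titration subject who stops on day 266 is followed to day 280, the last day of interval 10, with at most about a day spilling over. A 14-week subject is followed to day 308, the last day of interval 11. On that reading the nominal schedule shows little distortion, and weeks 45-48 are an empty row rather than a misleading rate.

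The table is also supplementary, SAP section 10 limits safety output to description, the main TEAE tables use other denominators, and off-drug events have their own table.

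All of this stands, and it limits the importance of the point. It does not remove the mismatch: the stated rule still puts subjects in the numerator whom it bars from the denominator. SAEs reported after the final visit can still fall where no denominator exists.

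A reader might infer that the last intervals will be inflated several-fold as a matter of course. The documents do not support that. Inflation of 3 times or more needs roughly 25% or fewer subjects extended with full 30-day capture, or about 5% extended with 14-day capture and visit-window spread.

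**Conclusion.** The point holds as a minor specification error. It does not depend on any scenario that SAP 10.2.2 can count an off-drug subject in the numerator and not in the denominator, or that nobody is on drug at the start of weeks 45-48.

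The size of the distortion in weeks 41-44 does depend on the scenario:

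- about 1.0 to 1.5 times on the nominal schedule with 14-day capture, provided no more subjects end titration at 12 weeks than at 14;
- about 1.3 to 3.9 times with visit windows and 14-day capture, for 5 to 60% extended;
- up to about 12 times with full 30-day capture, at the smallest extended share tabulated (5% at 12 weeks and 5% at 14). Smaller shares would give larger ratios on very few subjects.

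These figures assume a constant event rate and, for the last intervals, completers only. No endpoint, test or main safety table is affected.

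**What to change.** In SAP 10.2.2, limit the interval table to TEAEs with onset on or before the last dose date. Apply the same rule to the single-week OTTP rows for consistency; no material effect on those rows has been shown. Later onsets stay in the 30-day post-dose table that the next paragraph already plans, so nothing is lost. On-drug onsets then end within weeks 41-44, and the SAP should name that as the last interval.

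If post-dose events are to stay in the interval table, the denominator should also include subjects within 30 days of last dose at the start of the interval. Taking the 112 planned randomized subjects as completers for illustration, all 112 would be at risk in weeks 41-44. The current rule gives about 11 to 22 (10 to 20% of 112) when 10 to 20% have a 14-week titration. With an equal share at 12 weeks, weeks 45-48 would have about 22 to 45 at risk instead of none.

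The cost is one sentence of SAP text and minor programming. No data collection changes.
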